9.3.4.2 Surgery events

For all surgery events the following will be recorded, if available:

- Surgery description and indication (elective or emergency).
- Surgery type (minor or major surgery).
- Duration surgery hours (start and stop time of surgery).
- Haemostatic drug used in connection with surgery, beyond the monthly prophylactic rFXIII dose (covering other products and rFXIII, if used):
 - Drug name/product name.
 - Date and time of treatment

Protocol Date: 02 February 2016 Novo Nordisk Study ID: NN1841-3868 Version: 2.0

Final

40 of 65

 Study ID: NN1841-3868
 CONFIDENTIAL
 Version:

 UTN: U1111-1131-1558
 Status:

 EU PAS No.: ENCEPP/SDPP/3687
 Page:

• Dose and regimen.

- Haemostatic response during surgery (see section 9.3.4.2).
- Haemostatic response after surgery (see section 9.3.4.3).
- Blood products transfusion (yes/no):
 - Type (red blood cells, FFP platelets, or other).
- Adverse drug reactions, serious adverse events and medical events of special interest in connection with administration of the product.
- Allergic reactions (please refer to section 9.3.3.1).
- Embolic and thrombotic events (please refer to section 9.3.3.1).
- Lack of therapeutic effect (please refer to section 9.3.3.2), assessed as haemostatic response.

Definition of major surgery

Major surgery is any invasive operative procedure where any one or more of the following occur:

- A body cavity is entered.
- A mesenchymal barrier (e.g., pleura, peritoneum or dura) is crossed.
- A fascial plane is opened.
- An organ is removed.
- Normal anatomy is operatively altered.

These procedures may be performed using general anaesthesia, spinal anaesthesia, epidural anaesthesia, conscious sedation or with a combination of these modalities.

Definition of minor surgery

Minor surgery is any invasive operative procedure in which only skin, mucous membranes, or superficial connective tissue is manipulated. Examples of minor surgery include vascular cut down for catheter placement, implanting pumps or ports in subcutaneous tissue, biopsies or placement of probes, leads, or catheters requiring the entry into a body cavity only through a needle/guidewire.

Dental surgery will be classified as minor or major based on above definitions.

Haemostatic response during surgery

Clinical evaluation of haemostatic response during surgery will be evaluated as follows:

- **Excellent:** blood loss less than expected.
- Good: blood loss as expected.
- Moderate: blood loss more than expected.
- None: uncontrolled bleeding.

9.3.4.3 Post-surgery events

For all post-surgery events (1-10 days after surgery), the following should be recorded, if available:

• Haemostatic response after surgery (see section 9.3.4.3).

Protocol Date: 02 February 2016 Novo Nordisk Version: 2.0 Novo Nordisk

Status:

Page:

Final

41 of 65

UTN: U1111-1131-1558 EU PAS No.: ENCEPP/SDPP/3687

• Presence of wound haematoma (yes/no).

- Allergic reactions (please refer to section 9.3.3.1).
- Embolic and thrombotic events (please refer to section 9.3.3.1).
- Lack of the rapeutic effect (please refer to section 9.3.3.2), assessed as haemostatic response.
- Adverse drug reactions, serious adverse events and medical events of special interest.

Haemostatic response after surgery

Clinical evaluation of haemostatic response after surgery will be evaluated as follows:

- Excellent: better than expected in this type of patient and procedure.
- Good: as expected in this type of patient and procedure.
- **Moderate:** less than optimal for the type of procedure, maintained without change of treatment regimen.
- **None:** bleeding due to inadequate therapeutic effect with adequate dosing, change of regimen required.

9.3.5 Other assessments

9.3.5.1 Diary (instruction/evaluation)

A diary will be provided by Novo Nordisk if it's part of routine practice at the clinic/department. The patient will be instructed by the Physician on how to complete the diary. The following data on home treatment will be collected in the diary:

- Prophylactic treatment, on-demand treatment of bleed and prophylactic treatment related to surgery):
 - Product used (rFXIII or other).
 - Dose level.
 - Date and time of dose.
 - Information on whether the patient or the Physician decided regarding dose.
 - Cause.
- Body weight.
- Bleeding episodes (please refer to section 9.3.4.1):
 - Cause of bleed.
 - Onset of bleeding (date and time).
 - Arrest of bleeding (date and time).
 - Site of bleeding.
 - Severity.
 - Evaluation of achieved haemostasis.
- Allergic reaction.
- Embolic and thrombotic events.
- Lack of therapeutic effect.

Protocol Date: 02 February 2016 Novo Nordisk Version: 2.0

UTN: U1111-1131-1558

EU PAS No.: ENCEPP/SDPP/3687

CONFIDENTIAL

Status: Final
Page: 42 of 65

Medication error.

- Other disease than FXIII CD (any change or new diseases).
- Diary completed by whom and completion date.

The diary has special sections covering surgery. The patient will be asked to bring the surgery section to the surgery where a professional care provider will fill out pages regarding the surgery performed.

The patient will be asked to bring the diary to the site at each visit. The Physician will together with the patient review the diary entries and enter relevant information into the CRF. Review date of the diary and the Physicians' conclusion should be entered in the CRF. Study medication administration performed at home will be entered into the diary, and study medication administration performed at the hospital by the site personnel will be entered into the CRF.

9.3.5.2 Documentation of pregnancy

Patients must be instructed to notify the Physician immediately if they become pregnant. Documentation of the pregnancy should be obtained. The Physician must report any pregnancy reported during the study to Novo Nordisk (for more details see section 11.5). The outcome of the pregnancy will be followed up at one month post the predicted gestation date. If a patient's partner becomes pregnant, this should be handled according to section 11.5).

9.3.5.3 Collaboration with registries

Cooperation with other existing local FXIII or rare bleeding disorders registries in EU, US and other countries have been sought in order to collect data on all patients with FXIII CD regardless of treatment. As a result of this, contractual collaboration with the global Prospective Rare Bleeding Disorder Database (PRO-RBDD) has been established. Results from the non-interventional PASS (NN1841-3868) and PRO-RBDD will be included in the final study report. Patient participating in other registries e.g., PRO-RBDD will be identified in the CRF.

9.4 Data sources

It is the intention of this non-interventional study to observe routine treatment of the individual patient. Data and results available in the patient's medical record, in the patient diary and from assessments and laboratory sampling performed according to clinical practice at the participating sites will be recorded in the paper CRF. Information related to treatment and bleeding episodes will be captured in a patient diary by the patient or parent/caregiver. In case a patient is unable to enter a treatment or a bleeding episode in the diary, or is hospitalised, it should be reported in the patient record and subsequently in the paper CRF by the Physician. Further, contractual collaboration with the global Prospective Rare Bleeding Disorder Database (PRO-RBDD) has been established.

02 February 2016 | Novo Nordisk Protocol Date: 2.0

Final

Study ID: NN1841-3868 Version: UTN: U1111-1131-1558 Status: EU PAS No.: ENCEPP/SDPP/3687 Page: 43 of 65

9.5 Study size

No formal analysis of sample size has been conducted, but the adequacy of an expected number of patients has been considered.

Within Europe and the US, the study intends to recruit as many patients as possible among the FXIII CD patients treated with rFXIII. The total population in Europe of diagnosed patients with FXIII CD is between 300 and 400 patients, of which more than 10% are expected to receive rFXIII. Hence, in combination with the patients recruited outside Europe, a minimum of 30 patients are anticipated to be enrolled in the study.

Such an anticipated minimum number of patients are judged to facilitate a sufficient expansion to the safety experience of prophylactic treatment with rFXIII, taking into consideration the rarity of the disease.

Assuming that the recruitment rate is approximately constant and that the last patient is recruited at the end of the 4-year recruitment period, the expected average study participation will be approximately 4.5 years.

9.6 **Data management**

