4.10 Milestones

Planned date for FPFV: 17 May 2013

Planned date for last patient first visit (LPFV): 17 May 2017

Planned completion of the last patient (LPLV): 29 Jun 2019

Planned completion of non-interventional study report: 28 Dec 2019

Study ID: NN1841-3868 UTN: U1111-1131-1558 EU PAS No.: ENCEPP/SDPP/3687

CONFIDENTIAL

Date: Version: Status: Page:

02 February 2016 | Novo Nordisk 2.0 Final 14 of 65

Amendments and updates **5**

Amendment or update no	Date	Section of study protocol	Amendment or update	Reason
1	11-Jan- 2013	Section 2	For analysis of human EDTA plasma requires approximately 2 ml whole blood (0.5 1 ml EDTA plasma).	Change of collected volume of blood (optional blood sample) taken at the Visit 1 for FXIII activity samples from1 ml tube for the blood collection to 2 ml blood will need to be collected for the FXIII activity analysis
2	22-Jan-2014	Section 2.4 (section 8.1/visit procedures, 8.3/Assessments for safety and 15.2.3/Baseline characteristics) and accordingly in the flow chart section 2.2 (section 2	To collect blood samples for testing of anti-FXIII antibodies at visit 1 and at a visit to be conducted 1 year after entry of the patient into the study	FDA Post approval commitment to ensure data on FXIII antibody development from as many patients as possible
3	04-Feb-2014	Throughout the whole protocol	Withdrawn internally by Novo Nordisk. Main rationale for preparing this amendment was clarifications with regards to wording in the Updated Protocol, no. 2, dated 22 Jan 2014.	The changes from Amendment 3 have been implemented in Amendment 4.

CONFIDENTIAL

Protocol Study ID: NN1841-3868 UTN: U1111-1131-1558

EU PAS No.: ENCEPP/SDPP/3687

Version: Status: Page:

Date:

02 February 2016 | Novo Nordisk 2.0 Final 15 of 65

Amendment or update no	Date	Section of study protocol	Amendment or update	Reason
4	11-Aug-2014	Throughout the whole protocol	The main rationale for amending the protocol is due to EMA has published new requirements for non-interventional PASS (EMA/623947/20 12) studies regarding protocol format and content.	The update of the protocol to the EMA/PRAC (Pharmacovigilan ce Risk Assessment Committee) required protocol template is not a strict regulatory requirement, but is encouraged for PASS protocols submitted before 10 Jan 2013 (the original mentor TM 6 protocol was submitted to EMA for assessment in June 2012).

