			General updates since last protocol update 2 have been implemented in the updated protocol 3.	Please refer to page 3: Rationale for the Amendment
5	02 February 2016	Section 2 PASS information, Section 3 Responsible parties, Section 4.1 Title, Section 4.3 Primary endpoint, Secondary endpoints,	Recruitment period extended with 1 year to 17- May-2017. Definition of concomitant illness updated. Minor administrative changes implemented.	With the current recruitment rate it will not be possible to reach the anticipated number of 30 patients within the current recruitment period.

Protocol Study ID: NN1841-3868 UTN: U1111-1131-1558

EU PAS No.: ENCEPP/SDPP/3687

CONFIDENTIAL

02 February 2016 | Novo Nordisk 2.0 Final Date:

Version: Status: 16 of 65 Page:

Amendment or update no	Date	Section of study protocol	Amendment or update	Reason
		Section 4.5 Population, Section 4.8 Study size, Section 4.10 Milestones, Section 6 Milestones, Section 8.2.1 Primary endpoint, Section 8.2.2 Secondary endpoints, Section 9.1.1 Type of study, Section 9.1.2 Rationale for study design, Section 9.1.3 Treatment of patients, Section 9.3.2.7 Concomitant illnesses, Section 9.5 Study size, Section 9.7.2.2 Secondary endpoints.		Definition of concomitant illness aligned with other trials/studies in the project.

CONFIDENTIAL

Study ID: NN1841-3868 UTN: U1111-1131-1558 EU PAS No.: ENCEPP/SDPP/3687 Version: 2.0
Status: Final
Page: 17 of 65

6 Milestones¹

Milestone	Planned date
Start of data collection	17 May 2013
Defined as first entry of patient data	
Interim report 1	17 May 2015
Interim report 2	17 May 2017
End (or completion) of study	29 Jun 2019
Defined as the Last Patient Last Visit (LPLV)	
End of data collection	17 Aug 2019
Defined as the date from which the analytical dataset is completely available	
Registration in the EU PAS Register	28 May 2013
Final report of study results	28 Dec 2019
Planned completion of non-interventional study report	

Planned duration of recruitment period is 4 years after first patient first visit (FPFV) in the study.

All study visits should be performed according to normal local clinical practice. No additional visits should be conducted due to the participation in this study. It is recommended that assessment visits occur every one to six months depending on usual practice. The study will be terminated after 6 years; hereafter no more assessment visits will be performed.

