9.1 Study design

9.1.1 Type of study

This is a prospective, single-arm, multi-centre and multinational non-interventional PASS of safety related to treatment with rFXIII in patients with congenital FXIII A-subunit deficiency. No controls or blinding procedures are applied. There will be no dispensing of any study medication as part of this study. All direction for medication usage is solely at the discretion of the Physician in accordance with their usual care.

The non-interventional PASS will be accessible by all EU countries and other selected non-EU countries, where rFXIII is commercially available. The study duration is 6 years. During the conduct of the non-interventional study active follow-up with included sites will take place in order to ensure and maximise patient enrolment and retention and ensure that safety data are being collected and reported.

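### Section 9.5 states an average participation of about 4.5 years, but its own assumptions give 4.0 years

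*Protocol*

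**What the plan says.** Section 9.5 (Study size) gives no formal sample size calculation. It anticipates a minimum of 30 patients, judges that number sufficient in view of the rarity of the disease, and then adds a statement on follow-up. Its premise is: "Assuming that the recruitment rate is approximately constant and that the last patient is recruited at the end of the 4-year recruitment period". Its conclusion is: "the expected average study participation will be approximately 4.5 years".

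The timeline is set elsewhere in the protocol:

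- Section 6 (Milestones), on recruitment: "Planned duration of recruitment period is 4 years after first patient first visit (FPFV) in the study".
- Section 6, on the end of the study: "The study will be terminated after 6 years; hereafter no more assessment visits will be performed". It also asks for each patient's end of study visit within 3 months of study termination.
- Section 9.1.1: "The study duration is 6 years". Section 9.3.1.3 places the end of study visit 6 years after the first patient's first visit.
- Section 4.10 has the first patient entering on 17 May 2013 and the last one on 17 May 2017. For the close of follow-up it gives: "Planned completion of the last patient (LPLV): 29 Jun 2019".

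**The concern.** With entry spread evenly over a fixed period and a single closing date for all patients, average follow-up is the study length minus half the recruitment period. Section 9.5 supplies the recruitment pattern and the recruitment length, and the other sections supply the study length. The stated result does not follow from them.

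This is the only average-exposure figure in the protocol of a safety study whose primary objective is the incidence of specific adverse drug reactions. A reader who wants to know how much observation time 30 patients will provide has only this figure to work from, and it errs on the favourable side.

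**Working it through.** **Inputs**

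- Recruitment: constant rate over R = 4 years (Section 9.5 and Section 6; 17 May 2013 to 17 May 2017 in Section 4.10).
- Common end: T = 6 years after the first patient's first visit (Sections 6, 9.1.1 and 9.3.1.3).
- Sensitivity 1: end at the planned last patient last visit, 29 June 2019 (Section 4.10).
- Sensitivity 2: end at 17 August 2019, if every patient used the full 3-month window (Section 6).
- Dropout: no rate is stated, so taken as zero. Any dropout lowers the mean.
- Patients: 30, the anticipated minimum (Section 9.5).

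**Formula.** For uniform entry on [0, R] and a common end at T, mean participation = T − R/2.

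**Attempt to reproduce 4.5 years with R = 4**

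| End of follow-up | T (years) | Mean = T − 2 | Patient-years, n = 30 | Against 4.5 |
|---|---|---|---|---|
| 6 years after first visit | 6.00 | 4.00 | 120 | −11.1% |
| 29 June 2019 | 6.12 | 4.12 | 123.5 | −8.5% |
| 17 August 2019 (full window) | 6.25 | 4.25 | 127.5 | −5.5% |

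Patient-years and percentages are computed from the dates before rounding. Placing 30 patients at equal intervals from day 0 to year 4, which puts the last patient exactly at the end of recruitment as Section 9.5 assumes, also gives a mean of 4.0.

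**What would give 4.5**

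- R = 3, T = 6: 6 − 3/2 = 4.5 exactly. The amendment table in Section 5 records that the amendment of 2 February 2016 lengthened recruitment by 1 year, so the earlier period was 4 − 1 = 3 years. It lists Section 9.5 among the sections changed.
- R = 4 with T = 6.5: every patient would have to be followed 6 months beyond year 6. That conflicts with the 3-month window, with the planned last visit date, and with the 6-year maximum participation in Section 9.7.2.2.

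**Check on the minimum-participation proviso.** Section 9.3.1.3 makes the end of study visit conditional on 2 years of participation or 24 exposure days, whichever comes first. A patient who enters on 17 May 2017 completes 2 years on 17 May 2019, which is year 6. The proviso adds no time.

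**Illustration of the consequence.** The protocol states no patient-year total. Multiplying by 30, a mean of 4.5 years implies 30 × 4.5 = 135 patient-years, and 4.0 years gives 30 × 4.0 = 120. With zero events, the upper end of the exact two-sided 95% Poisson interval is 3.689 divided by the patient-years:

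- 3.689/135 = 2.73 per 100 patient-years
- 3.689/127.5 = 2.89 per 100 patient-years
- 3.689/120 = 3.07 per 100 patient-years

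The stated participation therefore makes the smallest excludable rate look smaller than it is.

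**The case against.** The best defence accepts the arithmetic and disputes the consequence. The study is purely descriptive, with no hypothesis tests and no formal sample size calculation. No enrolment target, interim report, analysis or stopping rule uses the 4.5 years. The primary endpoint is summarised as numbers of reactions and numbers and percentages of patients, not as rates per patient-year. All of this stands, and it limits the point to a minor one.

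A reader might infer that the judgement that 30 patients are enough rests on 4.5 years of follow-up and so falls with it. The text does not support that. In Section 9.5 the judgement comes before the participation sentence and is tied to the number of patients and the rarity of the disease. Section 4.8 makes the same judgement with no participation figure, and Section 9.1.2 justifies the duration by observation for up to 6 years.

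A reader might also treat 135 patient-years as the sponsor's claim, or the flat 11% as the shortfall. The first is only this review's multiplication by an anticipated minimum. The second is the largest value in a range that starts at 5.5% if the whole visit window is used.

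Finally, it is an inference that the figure was left over from the 3-year recruitment period. The exact match makes it probable, but the protocol's Section 9.5 as it stood before recruitment was extended is not available. The error does not depend on it, because the current text is inconsistent on its own terms. The word approximately does not cover a difference of half a year.

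**Conclusion.** The stated average is wrong. Under constant recruitment over 4 years and a common end at 6 years, mean participation is 4.0 years. It is 4.12 to the planned last patient last visit and 4.25 at the extreme of the visit window. No reading of the protocol's timeline gives 4.5.

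For the minimum of 30 patients, expected exposure is about 120 patient-years, and up to 127.5, against the 135 that 4.5 years would imply. These totals assume exactly 30 patients, a constant accrual rate as the protocol states, and no dropout. More patients would scale the totals but leave the percentage shortfall unchanged.

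The error is certain and its effect is small. It overstates expected exposure in the Study size section and changes no analysis.

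**What to change.** In Section 9.5, replace the average of approximately 4.5 years with approximately 4.0 years, before dropout. Optionally add that this is about 120 patient-years for 30 patients. A zero-event upper limit could be given as well, but the protocol's analyses do not need it.

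The cost is one line of text. Visits, data collection, analyses and timelines are unaffected; the only consequence is that the stated exposure becomes less favourable.

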9.6.1 Data management

Data management is the responsibility of Data Management, Novo Nordisk Headquarters. Data management may be delegated under an agreement of transfer of responsibilities to another data management unit within Novo Nordisk or Contract Research Organisation (CRO).

The patient and the biological material obtained from the patient will be identified by a patient number, study site, and study ID number. Appropriate measures such as encryption or deletion must be enforced to protect the identity of human patients in all presentations and publications as required by local/regional/national requirements. Appropriate measures such as encryption of data files must be used to assure confidentiality of patient data when it is transmitted over open networks.

Laboratory data will be transferred electronically from the central laboratory performing clinical analyses. The electronic laboratory data will be considered source data. In cases where laboratory data is transferred via non-secure electronic networks, data will be encrypted during transfer.

9.6.2 CRFs and rules for completing

Novo Nordisk will provide the CRFs. Print legibly using a ballpoint pen. Ensure that all questions are answered and that no empty data blocks exist. Ensure that no information is recorded outside the data blocks.

Protocol	Date:	02 February 2016	Novo Nordisk
Ctudy ID: MN11041 2060	Vargion:	2.0	

 Study ID: NN1841-3868
 CONFIDENTIAL
 Version:
 2.0

 UTN: U1111-1131-1558
 Status:
 Final

 EU PAS No.: ENCEPP/SDPP/3687
 Page:
 44 of 65

If a test/assessment has not been done and will not be available, indicate this by writing "ND" (not done) in the respective answer field in the CRF. If the question is irrelevant (e.g., is not applicable) indicate this by writing "NA" (not applicable) in the respective answer field. Further guidance can be obtained from the instruction in the CRF.

By signing the affirmation statement, the Physician confirms that the information is complete and correct

9.6.2.1 Corrections to CRFs

Corrections to the data on the CRFs must only be made by drawing a straight line through the incorrect data and by writing the correct value next to data that has been crossed out. Each correction must contain initials, date and explanation (if necessary) by the physician or the physician's authorised staff.

If corrections are made by the Physician's authorised staff after the date of the Physician's signature on the affirmation statement, the statement must be signed and dated again by the Physician.

Corrections necessary after the CRFs have been removed from the Physician's site must be documented on a data clarification form. Such corrections must be approved by the Physician or her/his authorised staff.

9.6.2.2 **CRF flow**

CRFs are produced on No Carbon Required (NCR) paper with one original and one copy. The top page (original page) of the CRFs is transferred by the monitor to the unit responsible for data entry as specified by Data Management, Novo Nordisk. One copy is to be archived with the Physicians study documentation.

Laboratory reports should preferably be signed and dated by the Physician on the day of the review of the analysis results and retained at the study site.

The results from the local laboratory should be entered in the CRF for each patient.

